9 STUDY MEASUREMENTS AND ENDPOINTS

9.1 Study endpoints

9.1.1 Primary endpoint

Differences in trabecular structure of subcutaneous tissue between the time prior to the multidisciplinary treatment and after the end of the treatment, assessed by skin ultrasound:

- Indented subcutaneous fascicles in the dermis (length: measured from the center of the base to the point of maximum indentation in the dermis)

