9.1.2 Secondary endpoints

- Changes in other skin structural parameters between the time prior to the multidisciplinary treatment and after the end of said treatment, assessed by skin ultrasound:
 - Thickness of skin: thickness of dermis, thickness of epidermis and total thickness of the skin
 - Changes in the echogenicity of the dermis
 - Presence of dermal edema
 - Presence of nodules in the subcutaneous areolar tissue

- Changes in cellulite severity in the areas involved, between the time prior to the multidisciplinary treatment and after the end of treatment, assessed from photographic images, using the validated photonumeric scale of Hexel et al.⁷, which evaluates the following parameters:
 - Number of visible depressions (0 = none, 1 = 1 to 4; 2 = 5 to 9; 3 = 10 or more depressions)
 - Depth of depressions (0 = No depressions; 1 = superficial depressions, 2 = medium depth depressions, 3 = deep depressions)
 - Morphology of the epidermis (0 = flat, 1 = "orange skin" look; 2 = "cottage cheese" look; 3 = quilted look)
 - Grade of laxity or sagging (0 = absence of laxity/sagging; 1 = slight; 2 = moderate; 3 = severe)
 - Severity in accordance with Nürnberg and Muller scale(0 = zero grade; 1 = first grade; 2 = second grade; 3 = third grade)

The addition of the scores obtained will provide a final score that will allow the cellulite classification:

From 1 to 5 = mild cellulite

From 6 to 10 = moderate cellulite

From 11 to 15 = severe cellulite

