10.2 Analysis of objectives

For the analysis of the primary objective, we will study the mean values of the trabecular structure and skin thickness, comparing the results before and after treatment. Similarly we will compare the scores of the photographic images (overall score and scores of each scale). Qualitative variables will be compared using Fisher's exact test, and the quantitative variables will be compared by means of the student's t test (in the case of 2 groups) or by the one-way ANOVA test (for 3 or more groups). If the conditions of the Student t test or the Anova test are not met, we will use the non-parametric test of the Mann-Withney U (2 groups) or the Kruskall-Wallis test (for 3 or more groups).

For all tests, the significance level will be set at $p < 0.05$.

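### Section 10.2 does not reserve the 5% level for the single primary endpoint: it places skin thickness under the primary objective and applies p < 0.05 to all 13 comparisons

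*Combined protocol and SAP*

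**What the plan says.** Section 9.1.1 names one measure under the primary endpoint: "Indented subcutaneous fascicles in the dermis (length: measured from the center of the base to the point of maximum indentation in the dermis". Section 9.1.2 lists the secondary endpoints. On ultrasound these are "Thickness of skin: thickness of dermis, thickness of epidermis and total thickness of the skin", then "Changes in the echogenicity of the dermis", "Presence of dermal edema" and "Presence of nodules in the subcutaneous areolar tissue". On photographs they are five items, each scored 0 to 3, and their sum. Sections 1.9, 1.10, 5.1 and 5.2 make the same division between objectives: trabecular texture is primary, skin thickness and photographic severity are secondary.

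Section 10.2 departs from this in three ways.

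- Its opening sentence puts the mean values of both trabecular structure and skin thickness into the analysis of the primary objective.
- It extends testing to every photographic score: "Similarly we will compare the scores of the photographic images (overall score and scores of each scale").
- It closes with one rule: "For all tests, the significance level will be set at" p < 0.05.

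Section 10 contains no testing order, no multiplicity adjustment and no statement that secondary results are exploratory. Section 7.5 calls the study an exploratory pilot, but only to explain why no sample size was calculated.

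**The concern.** A primary endpoint protects a conclusion only if the analysis section says that this test, and no other, carries the claim. Section 10.2 does not say so. Read as written, four measures could each be reported as a result on the primary objective, and any of 13 comparisons below 0.05 could be called significant without a qualifier. Section 4 sets out to evaluate the degree of benefit of the program, and section 13.4 plans publications and conference reports. A single photographic item at p = 0.04 could therefore be presented as a significant improvement, and nothing in the plan would mark it as one of many looks. The stated 5% would then not be the error rate of the study's conclusion.

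Several of the 13 are also not separate evidence. Total skin thickness contains the dermis and the epidermis, and the photographic total is the sum of its five items.

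**Working it through.** The plan has no derived figure to reproduce. The 0.05 is a chosen level, and the 30 women come without an effect size, a standard deviation or a power.

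**Count of comparisons**

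| Measure | Section | Number |
|---|---|---|
| Fascicle indentation length | 9.1.1 | 1 |
| Dermis, epidermis and total thickness | 9.1.2 | 3 |
| Dermal echogenicity | 9.1.2 | 1 |
| Dermal edema | 9.1.2 | 1 |
| Subcutaneous nodules | 9.1.2 | 1 |
| Photographic items | 9.1.2, 10.2 | 5 |
| Photographic total | 9.1.2, 10.2 | 1 |
| **Total** | | **13** |

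Under the primary objective as section 10.2 words it: 1 fascicle length + 3 thicknesses = 4.

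**Independent tests of true size 0.05, no real change**

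The chance of at least one p < 0.05 is 1 − 0.95^k.

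- k = 13: 1 − 0.95^13 = 1 − 0.513 = 0.487. Expected false positives are 13 × 0.05 = 0.65.
- k = 4: 1 − 0.95^4 = 1 − 0.8145 = 0.185.

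**Correlated endpoints, paired t tests**

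The documents give no correlations, so these are assumptions. Simulation: 30 women, 13 normal endpoints with equal correlation, two-sided 5% level (section 10.2 does not state the sidedness), 10,000 runs per setting.

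| Correlation between endpoints | Chance of at least one p < 0.05 |
|---|---|
| 0 | about 0.48 |
| 0.3 | about 0.42 |
| 0.5 | about 0.34 |
| 0.7 | about 0.25 |
| 0.9 | about 0.14 |

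A second simulation built the photographic total as the sum of its five items. With correlations of 0.3 to 0.7 among the photographic items and 0.3 to 0.5 among the ultrasound measures, the two sets being independent of each other, it gave 0.44 to 0.35.

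**If the t tests are run unpaired**

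Section 10.2 names the t test for two groups, with the Mann-Whitney test as fallback, and never says paired. The same simulation with unpaired t tests and 13 independent endpoints gave:

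- before/after correlation 0.5: per-test size about 0.007, chance of at least one about 0.08;
- before/after correlation 0.7: per-test size about 0.001, chance of at least one about 0.01.

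**After the fix**

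With one claim-bearing test at 0.05, the type I error of the claim is 0.05.

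**The case against.** The strongest case on the other side has four parts.

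*The primary endpoint is already separated.* Sections 9.1.1 and 9.1.2, and both statements of the objectives, divide primary from secondary. That is correct. A reader might infer that the protocol never separates them, and the documents do not support that. The failure is confined to section 10.2, but that is the section that governs the analysis.

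*The size is easily overstated.* A reader might infer that a false finding is close to a coin toss. The 49% needs 13 independent tests, and the overlap among these endpoints rules independence out, so 49% is a ceiling. A reader might also raise the count to 17 by adding hypodermis thickness and the presence and quantity of fibrous septa (section 9.2.4) and the clinical grade (section 9.2.2). Those are measured, but section 9.1 does not name them as endpoints. Thirteen is the count that the text supports. The absence of a control group does not enter this arithmetic either. It bears on whether a real change can be attributed to the program.

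*The tests as literally named may not have size 0.05.* This stands. Unpaired t tests on positively correlated data are conservative. Fisher's exact test is too: with 30 against 30 independent observations its true size is about 0.9% to 2.7% at assumed prevalences of 10% to 50%. But an unpaired analysis of before/after data is a fault that should be repaired, and once it is, the multiplicity applies at the sizes shown for paired tests.

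*An exploratory pilot needs no formal error control.* This also stands, and it limits the remedy. It does not remove the need to say that the results are exploratory, because the label in section 7.5 concerns sample size and not how p values are read.

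**Conclusion.** The point holds, and its place is section 10.2. The single primary endpoint named in section 9.1.1 is merged there with three thickness measures, and one unadjusted 0.05 rule covers all 13 comparisons.

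If no measure changes and the tests are correctly paired with true size 0.05, the chance of at least one significant result is at most about 49%, and about 42% to 25% at assumed between-endpoint correlations of 0.3 to 0.7. For the four measures under the primary objective it is at most 18.5%. The correlations are assumptions. With unpaired tests and assumed before/after correlations of 0.5 to 0.7 the 13-test figure falls to about 8% to 1%, so the figures above describe the plan once pairing is put right.

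This does not undermine the data collection. It decides which results may be stated as findings, and it should be settled before the images are read.

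**What to change.** In section 10.2:

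1. Delete skin thickness from the sentence on the analysis of the primary objective, and place it with the secondary analyses.
2. Replace the sentence on the significance level with wording such as: *The two-sided 5% level applies to one test only, the within-woman change in fascicle indentation length. All other endpoints are reported as the within-woman change with a 95% confidence interval. Any p values for them are labelled unadjusted and exploratory, and none supports a claim of effect on its own.*
3. In the same edit, specify paired methods for the before/after comparisons, so that the one claim-bearing test has its stated size.

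Holm or another formal adjustment across the secondary endpoints is not needed in this exploratory pilot, and the photographic items can still be reported under the exploratory label.

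The cost is a paragraph of wording, with no extra patients, visits or images. Section 10.1 already plans 95% confidence intervals for continuous variables. Section 9.2.4 has the ultrasound images assessed at the end of the study, so the change can be made before those results are known. The downside is that secondary results can no longer be presented as significant findings.

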11 REPORT OF ADVERSE EVENTS

The clinical evaluation of the subjects and safety of the multidisciplinary treatment is not the purpose of this study. Patients will only be visited before and after treatment. Therefore, no intermediate control will be performed to assess the safety and tolerability of the multidisciplinary anti-cellulite treatment during its application.

However, if patients report any adverse effects to the anti-cellulite treatment, the doctor will record it in the Data Collection Notebook, specifying:

- Type of reaction

- Intensity: mild (no limitation of daily living activities, patient may have mild discomfort), moderate (cause some limitation of daily living activities, patient may experience increased discomfort), severe (inability to perform daily living activities; patient may report intolerable pain or discomfort).
- Duration
- Causality with the DHA dietary supplement treatment under study: definitive, likely, possible, unlikely, unrelated, unknown.
- Therapy administered
- Resolution

If a subject reports a serious adverse event (see sidebar) during the time of this study, the physician should gather all available data and report them immediately (if possible within 24h.) by fax, telephone or e-mail to the Sponsor, who will implement the established Pharmacovigilance procedures in accordance with current legislation.

SERIOUS ADVERSE REACTION: is any adverse reaction that can be classified in one or more of the following categories:

- Lethal
- Life threatening
- It causes significant or persistent incapacity/ disability
- It causes hospitalization or prolongs hospitalization

Congenital anomalies/birth defects and serious adverse clinical consequences associated with use under conditions other than those set out in the Summary of Product Characteristics (SPC), overdose or abuse are also included.

Medical judgment should be applied when deciding whether an event or reaction is serious in other situations. Major adverse reactions or events that do not pose immediate threat to life, or do not cause death or hospitalization but may endanger the patient, should be deemed serious.

Sponsor:

[name]
PronoKal Group Medical Director
[name]
[name]
[contact]
[contact]

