7.7 Criteria for withdrawal or dropouts

Dropouts are those women who do not comply with the treatment schedule or do not complete treatment time established in the protocol of the multidisciplinary program.

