9.2.2 Follow-up of patients

Patient follow-up will be 10 ± 1 weeks to 18 ± 1 weeks, depending on duration of treatment depending on the degree of cellulite.

Only two controls will be performed: initial (prior to the multidisciplinary treatment) and final (after the end of the multidisciplinary treatment).

Initial visit

The inclusion and exclusion criteria will be assessed and the signed informed consent will be obtained. Demographic data (age) are recorded and the degree of cellulite is evaluated following the Nürnberg and Muller scale (0 = zero grade, 1 = first grade, 2 = second grade, 3 = third grade). The dermatologist will perform skin ultrasound and will take pictures.

Final visit

The dermatologist evaluations will be repeated: evaluation of the cellulite grade, accomplishment of skin ultrasound and photographic images.

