13 PRACTICAL CONSIDERATIONS

13.1 Workplan

The principal investigator will be in charge of including the patients referred to his office. Once the patient has read the Patient Information Sheet (Attachment 2) and confirmed their willingness to participate, the investigator will obtain the signature of the Informed Consent Form (Attachment 3) and must keep them with the rest of the documentation of every subject.

The doctor will record the data requested in the CRD and will perform the skin ultrasound and the taking of photographs. The ultrasound images will be saved digitally, identified by the patient and the visit code; and will be saved to be evaluated at the end of the study, blindly, by the principal investigator and by another evaluator separately. Similarly, the photographs will be saved in digital files identified with the patient and visit code. The latter will be recoded before evaluation by two independent evaluators to ensure the blindness of the patient and the visit in which the photographs were taken.

The investigator will not perform any clinical follow-up of the patients during the multidisciplinary medical treatment and will only visit the patients prior to and after the anti-cellulite program.

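### Adverse effects enter the record only when a patient reports them and no enquiry is scheduled, so tabulated frequencies would tend to undercount and would have no denominator of women asked

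*Combined protocol and SAP*

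**What the plan says.** Section 11 sets the scope first: "The clinical evaluation of the subjects and safety of the multidisciplinary treatment is not the purpose of this study". It adds that "no intermediate control will be performed to assess the safety and tolerability of the multidisciplinary anti-cellulite treatment during its application". It then gives the recording rule: "if patients report any adverse effects to the anti-cellulite treatment", the doctor enters it in the study notebook, with a list of details such as type, intensity, duration and causality. Serious events are also triggered by the patient: "If a subject reports a serious adverse event (see sidebar) during the time of this study".

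The study has two visits. Under Section 13.1 the investigator "will only visit the patients prior to and after the anti-cellulite program" and does no clinical follow-up in between. Section 9.2.2 gives the final visit as a repeat of the cellulite grade, the skin ultrasound and the photographs. No question on health problems is listed.

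Section 8 leaves prescription and control of the treatment to a physician, a physical trainer and dietitians acting independently of the study. It describes no route by which their observations would reach the study notebook.

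Section 10.1 plans descriptive statistics for all variables in the notebook, with frequency tables for nominal ones. Section 13.4 foresees publications and conference reports.

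**The concern.** The plan collects adverse effects and, by Section 10.1, would tabulate them, but no section makes anyone ask. A woman who had an effect and says nothing is then recorded in the same way as a woman who had none. Such a count tends to fall short, and a percentage from it has no proper denominator: 30 enrolled is not 30 asked.

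What is at stake is one descriptive table and any sentence in a report that rests on it. A reader who sees few or no adverse effects among 30 women could not tell a well-tolerated program from one in which nobody was asked. The limit applies to the whole program (both diets, exercise and cream). The ultrasound and photographic results are not touched.

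**Working it through.** The documents state no safety figure, and Section 7.5 gives 30 women without a calculation, so there is no planned figure to reproduce. The check has three parts.

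**1. The sections side by side.**
- Section 11: an event is recorded if the patient reports it.
- Section 9.2.2: the final visit has three listed activities, none of them an adverse-event enquiry.
- Section 10.1: everything in the notebook is tabulated.

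Followed as written, this gives a frequency table of spontaneous reports, with no count of women asked.

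**2. How far back an unprompted report must reach.** Phase lengths are from the Section 8 table. The two restructuring phases are ketogenic; drainage and toning are not.

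| Grade | Ketogenic days | Later days | Total |
|---|---|---|---|
| 1 | 7 + 14 = 21 | 20 + 20 = 40 | 61 |
| 2 | 14 + 7 = 21 | 30 + 30 = 60 | 81 |
| 3 | 20 + 20 = 40 | 40 + 30 = 70 | 110 |

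The final visit follows the end of treatment. For a woman who keeps to the schedule it therefore falls at least 40, 60 or 70 days after the ketogenic phase ends.

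**3. What zero recorded events could mean.** Input: n = 30 (Section 7.4).

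With every woman asked and every effect captured:
- one-sided 95% upper limit: 1 − 0.05^(1/30) = 0.095, or 9.5%
- two-sided exact (Clopper-Pearson) upper limit: 1 − 0.025^(1/30) = 0.116, or 11.6%

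Let c be the share of affected women whose effect is recorded. The documents do not give c; the values below are assumptions for illustration. The one-sided limit on the true rate becomes 0.095/c. If the true rate were 10% (also an assumption), the chance that nothing is recorded is (1 − 0.10 × c)^30.

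| Assumed c | One-sided 95% limit after 0 records | Chance of 0 records at a true rate of 10% |
|---|---|---|
| 100% | 9.5% | 4.2% |
| 75% | 12.7% | 9.6% |
| 50% | 19.0% | 21.5% |
| 25% | 38.0% | 46.8% |

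With passive reporting, c is unknown, so no row of this table can be claimed.

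**The case against.** The strongest reply is that the plan is open about its scope. Safety is disclaimed in Section 11, no objective or endpoint concerns it, and the women take the program whether or not they join the study. Nowhere do the documents treat an absence of reports as evidence of safety. All of this stands, and it keeps the point small. It does not remove it, because Section 10.1 would still tabulate what is collected.

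Several stronger readings are tempting and are not supported:
- *That nobody will be asked.* The text is silent; it does not forbid asking, and a report could be an answer to a question. The notebook itself is not among the documents, so it may contain a prompt.
- *That the woman must herself attribute the event to the program.* The recording rule speaks of effects of the treatment, but the causality field allows unrelated and unknown, and the serious-event sentence has no attribution condition.
- *That women who stop because of an effect never reach the final visit.* Section 7.7 only defines dropouts, as women who do not follow the schedule or "do not complete treatment time established in the protocol of the multidisciplinary program". It does not say whether they attend. The plan describes no other contact with them, but their absence is an inference.
- *That counts are too low by a stated percentage.* Any such figure is one minus an assumed reporting share.
- *That passive reporting alone prevents a conclusion of safety.* Even with complete capture, 0 of 30 does not exclude a rate near 10%.

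**Conclusion.** The point holds as a minor, inexpensive improvement. As written, the plan yields adverse-effect frequencies that are spontaneous reports, tend to undercount, and lack a denominator of women asked. It is a limit on what one table can support. It is neither a contradiction nor a miscalculation, and the efficacy analysis is unaffected.

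The size of the undercount is unknown. The 9.5% (one-sided) and 11.6% (two-sided) limits are best cases: they require all 30 women to be asked and to recall everything. The wider limits rest on assumed reporting shares.

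A reader might infer that the problem belongs to the 800–1200 kcal/day ketogenic diet. Section 8 confines that diet to 21 of 61, 21 of 81 or 40 of 110 days, whereas the recording rule covers the entire program. The ketogenic phase matters here only because it lies furthest from the final visit, so reports about it depend most on recall.

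**What to change.** At the existing final visit, ask every attending woman one open, non-leading question about health problems since the first visit. Record yes or no, and for a yes the details that Section 11 already lists. Report the number of women asked as the denominator.

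State two limits with the table. Women who do not attend are not covered, and answers about the ketogenic phase reach back at least 40 to 70 days, depending on grade. Because of these limits, the question narrows the gap but does not guarantee complete capture. Contacting non-attenders, or obtaining reasons for stopping from the prescribing physician, would be a new data route outside the two-visit design and is not part of this change.

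Before the causality item is used, reconcile it with Section 8. Section 11 asks about causality with a DHA dietary supplement, and the program described in Section 8 lists no such product.

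Cost: one question, one yes/no field and a count of women asked, with somewhat more events to record. No visit is added and no treatment rule changes.

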1.12 Therapy in study

Multidisciplinary program including diet, physical exercise and cosmetic cream (PnKCelulitis® program)

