3 GENERAL INFORMATION

Study title	Pilot study for ultrasound evaluation of structural changes in subcutaneous tissue in patients with cellulite after a multidisciplinary anti-cellulite treatment (PnKcelulitis® program). PROCESS study
Protocol Code:	PNK-CEL-2016-06
Type of study	A pilot, prospective, single blind, no controlled study with ultrasound evaluation of skin in patients undergoing treatment with a multidisciplinary program that includes diet, physical exercise and cosmetic cream.
Therapy in study	Multidisciplinary program including diet, protein supplements, physical exercise and cosmetic cream (PnKcelulitis® program)
Sponsor's details	PNKDIET, S.L.U. [name] [contact].
Principal investigator:	[name] Department of Dermatology. Hospital de la Santa Creu i Sant Pau
Research collaboration	[name] [name] Department of Dermatology. Hospital de la Santa Creu i Sant Pau
Primary objective	To evaluate the structural changes (trabecular texture) of subcutaneous tissue detected by skin ultrasound in patients with cellulite after a multidisciplinary treatment that includes diet, physical exercise and cosmetic cream.
Study population	Women with non-infectious skin cellulite (edematous fibrosclerotic panniculopathy), submitted to the PnKcelulitis® multidisciplinary program including diet, physical exercise and cosmetic cream.
No. of subjects	A pilot study is expected to include 30 patients
Follow-up	Patient follow-up will be 10 ± 1 weeks to 18 ± 1 weeks, depending on the degree of cellulite. With two controls: initial and final

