A wide range of therapies have been suggested for the treatment of cellulite, from weight loss (the most frequent), to treatments of skin massage and the use of topical agents and oral supplements. Massages reduce edema and there is also some evidence of increased collagen synthesis after such treatments. Likewise, their benefits might be explained by their likely effects on fibroblast activity stimulation and decreased adipocyte activity. Generally, topical creams contain different agents but have been poorly studied. Xanthines, botanical extracts, fragrances, and retinoid and PPAR receptors ligands seem to provide some results, through the reduction of adipogenesis and an increased thermogenesis that would improve microcirculation and the collagen synthesis. In addition, many oral agents for weight control (hydroxycitrate, epigallocatechin gallate, conjugated linoleic acid, etc.) are being researched and some of these agents, such as conjugated linoleic acid (CLA), seem to improve the signs of cellulite. Regular exercise and a proper diet can help control weight and therefore the appearance of cellulite.²

The PnKCelulitis® Program is a new treatment aimed at improving the signs of cellulite by combining different types of therapies. Its multidisciplinary approach includes: diet, physical exercise and the topical application of a cream. The dietary regimen includes a hypocaloric diet and protein supplements. The diet, which in the first few weeks is also ketogenic with a very restricted supply of carbohydrates, is able to increase lipolysis and reduce adipose tissue also improving fluid drainage. The supply of protein

supplements along with physical exercise seeks to increase muscle mass and reverse the underlying flaccidity, while improving microcirculation and mobilizing fat deposits. The treatment is complemented by the application of a cosmetic cream whose components contribute to reduce lipogenesis and improve circulation.⁵.

This study is aimed at evaluating the degree of benefit obtained through this new multidisciplinary anti-cellulite treatment, semi-objectively, from the changes observed in the dermis structure and the subcutaneous tissue by means of skin ultrasound⁶, as well as the visual changes on skin appearance in the areas involved.

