8 TREATMENT DESCRIPTION

Multidisciplinary program for the treatment of cellulite

The PnKCelulitis® Program consists of a multidisciplinary program that includes diet, protein supplements, physical exercise and anti-cellulite cream. Its duration depends on the degree of cellulite and is structured in 3 parts called "processes" (restructuring process, drainage process and toning process). Each of them consists of:

- Dietary regimen. The dietary regimen during the first part of the program (restructuring process 1 and 2) consists of a ketogenic low calorie diet (800-1200 kcal/day) based on protein, and vitamin and trace element supplement intake. The dietary regimen during the drainage and toning processes is based on a non-ketogenic low calorie diet (1,200 - 1,500 kcal/day) accompanied by protein products and vitamin and trace element supplements.
- Physical exercise. Toning exercises that increase in difficulty and intensity in each process.
- Application of a cosmetic cream. It is a cosmetic cream consisting of: red coralline algae, caffeine, red vine L-carnitine, and phosphatidylcholine.

According to the PnKCelulitis® program, the duration of the multidisciplinary treatment will vary between 61 days and 110 days, depending on the degree of cellulite assessed by the doctor who prescribes said treatment, according to the following scheme:

	Restructuring		Drainage	Toning
	1	2		
GRADE 1	7 days	14 days	20 days	20 days
GRADE 2	14 days	7 days	30 days	30 days
GRADE 3	20 days	20 days	40 days	30 days

Multidisciplinary treatment will be prescribed and controlled independently of this study by the prescribing physician as well as by the physical trainer and a team of dietitians from the Pronokal Group® Center. The doctor will be in charge to refer the patients to the Dermatology Service of the Santa Creu i Sant Pau Hospital to propose their participation.

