10 STATISTICAL ANALYSIS

10.1 Descriptive statistics

Descriptive statistic of all the variables collected in the Data Collection Notebook, with frequency tables for nominal variables and measures of central tendency and dispersion for the continuous variables. 95% confidence intervals (95% CI) will be estimated for the latter.

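### Section 11 asks for adverse-event causality against a DHA supplement that no description of the study treatment mentions

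*Combined protocol and SAP*

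**What the plan says.** Section 11 states that safety is not a purpose of the study and that there are no intermediate safety visits. It still sets a recording rule: "if patients report any adverse effects to the anti-cellulite treatment, the doctor will record it in the Data Collection Notebook". Six items follow: type of reaction, intensity, duration, causality, therapy administered and resolution. The causality item is "Causality with the DHA dietary supplement treatment under study: definitive, likely, possible, unlikely, unrelated, unknown".

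The treatment itself is described in four places. Section 1.12 gives diet, exercise and cream. Section 3 gives the same with protein supplements added. Section 4 says "Its multidisciplinary approach includes: diet, physical exercise and the topical application of a cream", and adds protein supplements under the dietary regimen. Section 8 is the fullest: "The PnKCelulitis® Program consists of a multidisciplinary program that includes diet, protein supplements, physical exercise and anti-cellulite cream". It goes on to specify vitamins and trace elements and to list the ingredients of the cream.

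On analysis, Section 10.1 plans "Descriptive statistic of all the variables collected in the Data Collection Notebook, with frequency tables for nominal variables".

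**The concern.** The causality item tells the doctor what to enter on a form, so its wording determines what the data mean. It names a product as the treatment under study, and that product is not described as part of the treatment.

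Two readings are open. Someone who follows the words rates the event against a DHA supplement. A reaction to the diet, the exercise or the cream could then be graded as unrelated, because no DHA product was identified. Someone who relies on the introductory sentence rates the same reaction against the program and might grade it as likely. Both answers would go into the same frequency table, and nothing else recorded would show which exposure was meant.

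Causality is also the only one of the six items that grades the relation between an event and the treatment. With visits only before and after the program, the protocol has no second causality assessment against which to check it.

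**Working it through.** This is a question of textual consistency, and the plan has no figure to reproduce. The check sets the causality item beside every description of the treatment.

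| Place | Treatment as named | DHA named? |
|---|---|---|
| Section 1.12 | Diet, exercise, cream | No |
| Section 3 | Diet, protein supplements, exercise, cream | No |
| Section 4 | Low-calorie diet with protein supplements, exercise, cream | No |
| Section 8 | Ketogenic then non-ketogenic low-calorie diet; protein products; vitamins and trace elements; toning exercise; cream with listed ingredients | No |
| Section 11, up to and including the sentence before the list | The program, under three general names | No |
| Section 11, causality item | DHA dietary supplement | Yes |

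1. **Mentions of DHA.** There is one in the available text, in the causality item. Section 4 names other oral agents, such as conjugated linoleic acid, but only as background on cellulite therapies.

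2. **Consistency within Section 11.** The section refers to the treatment as multidisciplinary, as multidisciplinary anti-cellulite and as anti-cellulite, once each, making three references to the program. It refers to a DHA supplement once. The third program reference is in the sentence that governs the list.

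3. **Could missing text explain it?** The causality sentence is complete, with no sign of redaction. Judging by the Index, the parts not available are identification sections of the abstract (among Sections 1.2 to 1.7) and Section 10.3, on responsibility for the analysis. Their titles do not suggest a treatment description. The attachments and the Data Collection Notebook were not available.

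4. **Size.** Items recorded per adverse effect = 6; items affected = 1; 1/6 = 17%. Within that item, the share of ratings made against the wrong exposure runs from 0% (always read as the program) to 100% (always read literally). The documents do not give the number of adverse events, so no count can be attached.

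5. **Reach.** The other five items do not name an exposure. The objectives (Section 5) and endpoints (Section 9.1) do not use causality. For serious events, "the physician should gather all available data and report them immediately" to the sponsor is not made conditional on the causality rating. Section 11 does move between event and reaction in its wording on serious cases, but it does not refer back to this item. The analysis affected is the descriptive tabulation in Section 10.1.

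**The case against.** The case for treating this as trivial has five parts.

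- **Context corrects it.** Only effects of the anti-cellulite treatment are recorded, the item itself speaks of the treatment under study, and Sections 1.12 and 3 define that therapy as the program. Many doctors would infer the intended exposure. This stands, and it makes the 100% end of the range a logical limit, not an expectation. A form should still not depend on the person completing it setting its words aside.
- **There may be one main rater.** Sections 9.2.1 and 13.1 point to a single dermatology department with the principal investigator in charge of inclusion. Disagreement between raters is then less likely. That narrows one route to inconsistency, but a single doctor following the literal wording is enough to misdirect the ratings.
- **Safety is not a purpose, and the 17% counts list items, not harm.** Both points are fair and limit the weight of the finding. The plan nevertheless collects the variable and tabulates it.
- **The Notebook has not been seen.** If its field is worded correctly, the effect on recorded data could be nil. This stands, so confidence attaches to the mismatch in the protocol and not to a proven effect on the data.
- **A supplement might contain DHA.** The ingredients of the supplements are not listed, so this cannot be excluded. Even then, the item would cover one undescribed component of a program with several, and the wording would still be wrong.

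**Conclusion.** The concern holds. As written, the item directs causality ratings at an exposure that the protocol does not describe as part of the treatment, and it contradicts the sentence that introduces it. Ratings may refer to the wrong exposure or may not share one meaning.

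The consequence is confined to one recorded variable and its frequency table; the efficacy analyses are untouched. The text should be corrected, although it does not threaten the study's conclusions.

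The conclusion assumes that the unavailable sections and attachments do not define a DHA product as part of the program. It does not claim that DHA is absent from every product used. The wording may have been carried over from another protocol, but the documents do not establish that.

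**What to change.** In Section 11, reword the item as causality with the PnKCelulitis multidisciplinary program under study and keep the six response levels as they are. Check the corresponding field in the Data Collection Notebook and correct it if it carries the DHA text.

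The sponsor should also confirm whether any product in the program contains DHA as a supplement. If one does, Section 8 should say so, so that the two sections describe the same treatment; the causality item should still refer to the whole program.

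The cost is one line in Section 11 and, if needed, one form field and one sentence in Section 8. No visit, patient or analysis is added.
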